6.4 Sample Size and Power

Based on power analysis²⁶ and a recent study of youth sleep and daily mood,²⁰ which detected a medium effect of nighttime sleep on daily mood, a total of 25 participants are needed across 14 days to detect medium (.35 to .45) daily effects of sleep on mood with 80% power and a p-value of <.05. To compare the two study groups (7-day and waitlist control) on the effects of Beds for Kids, 24 subjects (12 per group) are needed to detect an effect size of .45 with 80% power and a p-value of <.05, using repeated measures analysis of variance, 14 measures per subject, and a correlation of 0.5 among repeated measures. Our proposed sample of 50 caregiver-child dyads is thus sufficient, and will accommodate analyses for Aims 2 and 3.

A total of 5-10 qualitative interviews are needed to accommodate analyses for Aim 4. This sample size was based on semi-structured interview guidelines for qualitative research.⁴⁷

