This is a randomized controlled trial (RCT). Caregiver-child dyads will be assigned to the intervention group, in which they receive a bed through the Beds for Kids program after a 7-day period, or to the waitlist control group, in which they receive a bed after a 14-day period.

Setting/Participants:

This is a single site study to be performed at CHOP. A total of 50 caregiver-child dyads (child age 2 to 5 years) will be recruited from clinicians at CHOP primary care sites. Families must be eligible for the Beds for Kids program: (a) child is living without his/her own bed and (b) family is at or below 100 percent of the Federal Poverty Guideline.

Study Interventions and Measures:

Caregivers in the intervention and waitlist control conditions will complete measures of child sleep and behavior, as well as caregiver functioning (mood; resilience; sleep) and family functioning (i.e., chaos). Over a 14-day period, children in both study conditions will wear actigraphs to objectively measure sleep, and caregivers will complete daily ratings of child behavior, caregiver mood, and caregiver sleep. At one-month after bed delivery, caregivers will complete measures of child sleep and behavior. At one-month follow-up,

[figure not shown]
caregivers will also be given the option to participate in a brief, semi-structured qualitative interview related to barriers to and facilitators of sleep health and behavioral sleep treatment.

The primary study outcome is the difference between study conditions in actigraph-derived and caregiver-reported child sleep (bedtime, bedtime variability, sleep quality, night wakings, total sleep duration) for days 7 to 14 (bed vs control), as well as compared to baseline. Thus, this is a mixed between (bed vs waitlist) and within (days 1-7 vs days 8-14) group design.

TABLE 1: SCHEDULE OF STUDY PROCEDURES

Study Phase	Screening															One month Follow-up	
Visit Number	0	1	2	3	4	5	6	7	8	9	10	11	12	13	14	15	16
Approximate Study Days (May vary by 7 days)	0	1	2	3	4	5	6	7	8	9	10	11	12	13	14	15	36-43 (dependent on bed delivery date)
Chart review	X																
Verbal Informed Consent	X																
Review Inclusion/Exclusion Criteria	X																
Randomization	X																
Caregiver-reported caregiver and family demographic information		X															
Caregiver-reported child sleep and behavioral measures, caregiver resilience, mood, and family chaos measures		X															X

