Medical record review and child demographic data abstraction		X															
Actigraphy (objective sleep measurement)			X	X	X	X	X	X	X	X	X	X	X	X	X	X	
Caregiver-reported daily questionnaire (caregiver and child sleep and mood)			X	X	X	X	X	X	X	X	X	X	X	X	X	X	
Bed provision (day 7 for intervention group; day 14 for waitlist control group)									X							X	
Caregiver semi-structured interview about barriers to and facilitators of sleep health and behavioral sleep treatment																	X
Adverse Event Assessment	X	X	X	X	X	X	X	X	X	X	X	X	X	X	X	X	X

FIGURE 1: STUDY DIAGRAM

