3 INVESTIGATIONAL PLAN

3.1 General Schema of Study Design

3.1.1 Screening and Randomization Phase

Clinicians at the Chestnut Hill, South Philadelphia, Karabots, and Cobbs Creek locations who are already referring families directly to the Beds for Kids program will identify potentially eligible families for this study. Families who are eligible for Beds for Kids will then be asked whether they would be interested in participating in a research study related to the program. The clinician will provide the name, MRN, and contact information of interested families to the study team. The study team will then conduct an initial medical record review to identify whether the referred family is potentially eligible. The study team will then contact the potentially family to initiate informed consent and eligibility screening procedures. Alternatively, families receiving care at any of the CHOP primary care recruitment sites (Chestnut Hill, South Philadelphia, Karabots, or Cobbs Creek) may self-refer to the study if they hear of the Beds for Kids program through word-of-mouth or social

media (e.g., Facebook). However, we will not advertise the study on social media of any kind for recruitment purposes.

The informed consent process will take place by phone, with a member of the study team obtaining verbal consent from the legal guardian for study participation. Child assent will not be obtained as all participating children are under age 5 years. Families will be informed that they are free to decline to participate or to withdraw from the study, and that this will not impact their participation in the Beds for Kids program or any future medical care. After obtaining verbal informed consent, families will be screened for study inclusion and exclusion criteria.

Eligible families will be randomly assigned to receive a bed from Beds for Kids 7 days after initiating the actigraph/daily diary study procedures (intervention condition), or to receive a bed 14 days after initiating these procedures (waitlist control condition). Thus, this is a mixed between (bed vs waitlist) and within (days 0-7 vs days 8-14) group design.

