6.3.2 Efficacy Analysis

The primary analysis will be based on an intention to treat approach and will include all randomized subjects. To evaluate the impact of provision of a child bed through the Beds for Kids program on child sleep (Hypothesis 1a), we will compare children in the study condition who received a bed at day 7 to those in the waitlist control condition (bed at day 14) on objectively and subjectively measured sleep variables using two-level multilevel mixed models. Multilevel models allow for an examination of both within-child (daily assessments, level 1) and between-child (level 2) associations between sleep and daily child and/or caregiver functioning.²⁰ Child age, sex, baseline caregiver mood and resilience, and family chaos as level 2 covariates, given research showing that these variables impact child sleep. ^{7, 9, 12} To examine whether children who receive a bed at day 7 show improved behavior, increased caregiver mood, and better caregiver sleep relative to children in the waitlist condition (Hypothesis 1b), we will run three different multilevel mixed effect models, using child daily behavior, caregiver mood, and caregiver sleep scores as the outcomes, respectively. Analyses will include child sleep location, age, sex, baseline caregiver mood and resilience, baseline family chaos, and baseline child internalizing and externalizing behavior at model level 2 as covariates.

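### The Hypothesis 1a model in 6.3.2 omits the post-bed, baseline-referenced contrast that the abstract makes primary, and the 24 in 6.4 appears to size a different test

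*Combined protocol and SAP*

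**What the plan says.** The abstract sets the primary outcome as the difference between conditions in child sleep "for days 7 to 14 (bed vs control), as well as compared to baseline" and concludes that "this is a mixed between (bed vs waitlist) and within (days 1-7 vs days 8-14) group design". Section 3.1.1 repeats the design with another first window: "mixed between (bed vs waitlist) and within (days 0-7 vs days 8-14) group design". Section 6.1 speaks only of change in sleep. Hypothesis 1a in 2.1 names only the comparison with waitlist.

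For Hypothesis 1a, section 6.3.2 says "we will compare children in the study condition who received a bed at day 7 to those in the waitlist control condition", using two-level mixed models of daily data, with "Child age, sex, baseline caregiver mood and resilience, and family chaos as level 2 covariates". It mentions no period, no restriction to nights after delivery and no earlier value of the sleep outcome. Elsewhere in 6.3.2 such terms do appear: Aim 2 is restricted to week 1 because neither arm has a bed then, and Aim 3 regresses follow-up sleep on baseline sleep.

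Section 6.4 states that "24 subjects (12 per group) are needed to detect an effect size of .45 with 80% power" at p < .05, "using repeated measures analysis of variance, 14 measures per subject, and a correlation of 0.5 among repeated measures", and concludes that 50 dyads are enough. It does not say whether .45 is Cohen's f or a difference in SD units, or whether the effect is the arm main effect or an interaction.

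**The concern.** The arms are treated alike until the intervention arm receives its bed, about halfway through the 14 nights. A model with an arm term and no period term leaves open an arm effect averaged over all nights, about half of which carry no treatment difference. It also leaves unused the week-1 nights that would serve as each child's own reference. If 6.4 was computed for that averaged effect, its power statement belongs to a different test from the one in the abstract. Families are not blinded and there are several sleep outcomes, so the choice of contrast should not be left until the data are in hand.

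**Working it through.** **Inputs.** From 6.4: effect size .45, alpha .05, m = 14 measures, correlation ρ = .5, N = 24 and N = 50. From 6.3.2 (Aim 2): no bed in either arm in week 1. From 5.1.2: at least 10 usable days, allowing for 4 missing. Assumed here: single-night SD of 1, equal arms, and the AR(1) values of .5 and .8 and equal correlation of .2 used as sensitivity.

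**1. Reproducing the 24.** Between-arm test: λ = f²·N·m/(1+(m−1)ρ), with 1 and N−2 df.
- f = .45, N = 24: .2025×24×14/7.5 = 9.07, power .821. At N = 22, λ = 8.32, power .783. So 24 is the smallest even N.
- .45 read as SD units (f = .225): N = 86.
- Arm-by-time interaction, λ = f²·N·m/(1−ρ), with m−1 and (N−2)(m−1) df: N = 6 (f = .45) or 14 (f = .225).

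Only the all-nights arm effect at f = .45 gives 24.

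**2. What that test does with a post-bed effect.** Assume that f = .45 (0.90 SD) holds on 7 bed nights only; 6.4 does not say this. Averaged over 14 nights the effect is 0.90×7/14 = 0.45 SD, or f = .225. At N = 50, λ = .050625×50×14/7.5 = 4.73, power 57%. At equal correlation .2 it is 87%. Under AR(1) of .5 or .8 it is 94% or 64%.

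**3. Post-bed nights alone, .45 read as f.** With 7 nights at ρ = .5, λ = .2025×50×7/4 = 17.7, power 98.5% at N = 50.

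**4. Post-bed nights, effect of 0.45 SD, N = 50, 7+7 nights.** Let V1 and V2 be the variances of a child's week-1 and week-2 means and C their covariance. The week-1-adjusted variance is V2 − C²/V1. At equal correlation .5, V1 = V2 = (1+6×.5)/7 = .571 and C = .5, so the adjusted variance is .571 − .25/.571 = .134.
- Post-bed only: λ = .45²×50/(4×.571) = 4.43, 48 df, power 54%.
- Adjusted, with inflation 1+1/(N−4) = 47/46: λ = .45²×50/(4×.134×47/46) = 18.5, 47 df, power 98.8%.

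| Correlation | Post-bed only | Week-1-adjusted |
|---|---|---|
| Equal, .5 | 54% | 98.8% |
| AR(1), .5 | 75% | 75% |
| AR(1), .8 | 50% | 56% |

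**5. Difference detectable with 80% power at N = 50.** The same formula is solved for the difference. The 5+5 case uses nights 1–5 and 8–12.

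| Contrast | Equal correlation | AR(1) .5 to .8 |
|---|---|---|
| Week-1-adjusted | 0.30 SD (.5, 7+7); 0.35 (.5, 5+5); up to 0.41 (.2, 5+5) | 0.48 to 0.66 SD |
| Change (arm-by-period) | 0.31 to 0.46 SD (.5, 7+7 to .2, 5+5) | 0.63 to 0.80 SD |

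The five level 2 covariates of 6.3.2, if they explain nothing, move 0.299 to 0.318 SD.

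**6. Windows.** The abstract has days 7 to 14 and also days 1–7 against 8–14; 3.1.1 has days 0–7. Sections 4.2 and 4.2.1 count delivery on days 7 and 14 from actigraph initiation. Table 1 marks actigraphy from Visit 2 (study day 2) and beds at Visits 8 and 15. On the actigraph scale, if delivery-day nights count as bed nights the arms differ on nights 7–13; if not, on nights 8–14. Either way 7 nights differ, and a window of days 7 to 14 holds 8.

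**The case against.** Section 6.3.2 does not prescribe pooling all nights; it is silent, and an analyst who had read the abstract might add the period term. That is fair, and a reader should not infer that an all-nights test is planned. The 57% in step 2 describes one test the text leaves open, and it assumes that .45 refers to bed nights only.

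A reader might also infer that 24 is an arithmetic error. It is not: it is correct for the test it fits. Nor is the source certain. A week-1-adjusted contrast of 0.45 SD at correlation .5 also happens to need 24 (power .800), as does f = .45 over 8 post-bed nights (.802). The all-nights reading is preferred only because 6.4 specifies repeated-measures ANOVA with 14 measures and mentions no split into periods.

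The strongest objection concerns consequence. The gap between 54% and 98.8% comes from equal correlation .5 and disappears at AR(1) .5. So naming the contrast and metric does not by itself settle whether 50 dyads suffice. That stands. Part of the window discrepancy is also a matter of two day scales: in study days, days 1–7 against 8–14 agrees with the bed marks in Table 1. The other two wordings still need reconciling.

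**Conclusion.** The concern holds in limited form. The contrast that the abstract makes primary is absent from the Hypothesis 1a model, and 6.4 gives a sample size for an unnamed effect in an unnamed metric that best matches an arm effect over all 14 nights. The first part is read directly from the text; the second is an inference from the arithmetic.

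A reader might conclude that the trial is underpowered. The documents do not support that. If .45 is f, post-bed nights alone give 98.5% power at 50 dyads with equal correlation .5. If it is in SD units, power for the week-1-adjusted contrast with 7+7 nights runs from 56% (assumed AR(1) .8) to 98.8% (equal correlation .5), and the documents give only the single value .5. What is established is that 6.4 does not support its conclusion for the contrast in the abstract. This should be fixed; it does not call the sample size into question by itself.

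**What to change.** **Section 6.3.2.** Name the primary test for Hypothesis 1a as the arm difference on post-bed nights, adjusted for the child's own week-1 mean of the same outcome. The same form can serve the daily outcomes of Hypothesis 1b. Do not treat an arm-by-period change contrast as interchangeable: it is nearly as precise at equal correlation .5 but less so when correlation is low or decays (step 5). Reconcile the three window wordings with the two day scales, use one window in both arms, and say how the nights of the delivery days count.

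**Section 6.4.** State the metric of .45. Replace the 24-subject sentence with the difference detectable with 80% power at 50 dyads for the week-1-adjusted contrast, labelling the correlation as an assumption: 0.30 SD at correlation .5 with 7+7 nights and 0.35 SD with 5+5. Give as sensitivity up to 0.41 SD at equal correlation .2, and 0.48 to 0.66 SD under an assumed AR(1) of .5 to .8.

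**Cost.** Text changes only. Week-1 nights are already collected in both arms; no subjects, nights or measurements are added.

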6.5 Interim Analysis

There will not be an interim analysis as this study does not involve a life-threatening condition or a life-threatening outcome.

7 STUDY MEDICATION (STUDY DEVICE OR OTHER STUDY INTERVENTION)

7.1 Description

7.1.1 Packaging

The intervention for this study is involvement in the Beds for Kids program, through the non-profit organization One House at a Time (OHAAT). The program provides each child with a new twin mattress, a bedframe, and a "bedtime bag," which contains a sheet set, blanket, pillow, several books, stuffed animal, and toothbrush. Children also receive educational messages about healthy sleep habits (3 messages: bedtime before 9:00 PM; no caffeine; no electronics in the bedroom) via a magnet and "color-your-own" bookmark. In a previous study, healthy sleep education was associated with increased nighttime sleep duration and fewer electronic items in the child's bedroom. All of the items are sorted, packaged, and delivered directly to program recipients by OHAAT members and volunteers.

7.1.2 Treatment Compliance and Adherence

Treatment compliance and adherence will be monitored by Lead Investigator [name] through contact with the Beds for Kids program. However, no members of the Beds for Kids program will have access to any study data from participants. [name] will monitor bed delivery scheduling and physical bed delivery in her capacity as Board Member of this organization.

8 SAFETY MANAGEMENT

8.1 Clinical Adverse Events

Clinical adverse events (AEs) will be monitored throughout the study.

8.2 Adverse Event Reporting

Since the study procedures are not greater than minimal risk, SAEs are not expected. If any unanticipated problems related to the research involving risks to subjects or others happen during the course of this study (including SAEs) they will be reported to the IRB in accordance with CHOP IRB SOP 408: Unanticipated Problems Involving Risks to Subjects. AEs that are not serious but that are notable and could involve risks to subjects will be summarized in narrative or other format and submitted to the IRB at the time of continuing review. Note that any AE related to the provision of the bed will be under the purview of Beds for Kids, and are not part of the procedures of this study.

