Beds for Kids issue. If families encounter any difficulty with materials provided to them through Beds for Kids (e.g., mattress, bedframe), the family will be asked to contact Beds for Kids directly. We will inform families that in order to maintain their confidentiality and privacy in the study, we are unable to contact Beds for Kids on their behalf.

Other follow-up issue. If caregiver-child dyads that participated in the study contact the [name] (PI) or [name] (investigator) by phone to request follow-up, any issues will be handled via phone, without an in-person visit.

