4.5 Subject Completion/Withdrawal

Subjects may withdraw from the study at any time without prejudice to their care. They may also be discontinued from the study at the discretion of the Investigator for lack of adherence to study treatment or visit schedules, or AEs. The Investigator may also withdraw subjects who violate the study plan, or to protect the subject for reasons of safety or for administrative reasons. It will be documented whether or not each subject completes the clinical study. If the Investigator becomes aware of any serious, related adverse events after the subject completes or withdraws from the study, they will be recorded in the source documents and on the CRF.

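### Section 8.2 hands adverse events related to the bed to the charity, although the bed program is the study intervention, so recording and reporting them as study events is not assured

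*Combined protocol and SAP*

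**What the plan says.** **What is tested.** Section 7.1.1: "The intervention for this study is involvement in the Beds for Kids program". It lists the mattress, frame, bedding and other items, and the sleep messages. Section 3.1.1 describes the allocation: "Eligible families will be randomly assigned to receive a bed from Beds for Kids 7 days after initiating" the actigraph and diary procedures, against 14 days for the waitlist arm.

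**How AEs are handled in general.** Section 8.1: "Clinical adverse events (AEs) will be monitored throughout the study". Section 5.4 bases safety monitoring on AEs together with the child behavior and caregiver mood scales. Table 1 marks an AE assessment in every visit column from 0 to 16. Section 8.2 sends unanticipated problems related to the research (SAEs included) to the IRB under a named SOP. Non-serious but notable AEs go to the IRB at continuing review.

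**The exception.** Section 8.2 closes with a carve-out: "any AE related to the provision of the bed will be under the purview of Beds for Kids". The same sentence goes on to place these events outside what the study itself does.

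**Related provisions.** For trouble with the mattress or frame, section 4.4 says "the family will be asked to contact Beds for Kids directly", and the team will not approach the charity for them. For serious, related AEs that the investigator learns of after completion or withdrawal, section 4.5 says "they will be recorded in the source documents and on the CRF". Section 9.4.1 sets a monthly check-in with the charity's executive director about concerns reported to its staff.

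**The concern.** The bed is inside the study when benefit is assessed and outside it when harm is assessed. The primary comparison is bed against no bed in the second week, and section 9.4.3 names the bed as a direct benefit of taking part. Yet the only reporting rule that mentions the bed takes AEs related to it out of the study.

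The participants are children aged 2 to 5 who receive a twin mattress on a metal frame. If one were hurt in connection with the new bed, staff following 8.2 could properly leave the event out of the study record and out of the reports to the IRB. What is at stake is the completeness of the AE record for the randomised intervention, and the risk-benefit statement in section 9.4.4 that depends on it.

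**Working it through.** No formula applies: the plan states no AE rate, safety sample size or safety threshold on this point. The check sets the provisions side by side.

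1. **Is the bed the intervention?** Yes. Section 7.1.1 says so, and section 3.1.1 randomises when it arrives. Both arms get a bed, so what is allocated is timing, but in the second week the contrast is bed against no bed.

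2. **Do the general AE provisions make an exception for the bed?** No. Sections 8.1 and 5.4 contain none. Table 1 marks AE assessment in 17 columns (visits 0 to 16: 16 + 1 = 17), including columns after delivery.

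3. **Which rule governs a bed-related event?** Sections 8.1 and 5.4 are general. The last sentence of 8.2 is specific and comes after the general reporting rules in that section. On a plain reading the specific sentence prevails, so such an event need not be handled as a study AE.

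4. **Do other provisions restore it?**
   - Section 4.4 directs families with bed problems to the charity. It concerns materials and does not stop a family from mentioning an injury on a study call, but it sets no recording duty either.
   - The check-in in section 9.4.1 could bring an event to light, but no duty to record it as an AE is stated. Section 9.3 bars giving the charity identifying information on families, so linking a report to a participant is not assured.
   - Section 4.5 covers only serious, related events learned of after completion or withdrawal. Whether a bed event counts as related is unclear while 8.2 stands.
   - Section 6 plans no AE summary in which an omission would show.

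5. **Is harm weighed as benefit is?** No. Section 9.4.3 counts the bed as a benefit. Section 9.4.2 covers questionnaires, interviews and confidentiality only.

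6. **How would recorded events need to be shown?** Table 1 marks delivery at visit 8 (intervention) and visit 15 (waitlist). Scheduled AE assessments after the delivery visit number 16 - 8 = 8 in the intervention arm and 16 - 15 = 1 in the waitlist arm. Counts by arm alone would mix different opportunities to report, so time relative to delivery is needed as well.

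**The case against.** The best defence is that the bed is an existing charity service. Clinicians already refer families to it, declining the study does not affect access, and section 3.1.1 says delivery usually takes 1-2 weeks and is not delayed by the design. On this view 8.2 only says who answers for the product and that delivering it is not a research procedure. It does not literally say that events go unrecorded, and the named SOP, which is not in the documents, may cover them. The study is minimal-risk and has no safety endpoint.

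Part of this stands. It explains why the sentence was written and rules out several stronger readings that a reader might infer:

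- **That a bed-related harm has no way into the record, or that every such event is lost.** Assessments run from visit 0 to visit 16, the team calls daily during visits 2 to 15, there is a monthly check-in, and section 7.1.2 has the Lead Investigator follow delivery through contact with the charity. Knowledge of an event is likely enough; what is unsettled is what must then be done with it.
- **That the children get a new bed only because of the trial.** The trial sets the timing within usual program practice.
- **That a report of no AEs would be true by definition.** Events unrelated to the bed, such as distress from questionnaires, would still count.
- **That the small sample is the measure of the fault.** With so few children, uncommon harms could not be excluded with or without the carve-out.

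The defence does not remove the conflict. A pre-existing service that a trial adopts as its intervention and randomises is still the trial's intervention, and a rule that needs charitable reading to keep its harms in the record should be rewritten.

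**Conclusion.** The contradiction is real and should be corrected. Section 8.2, followed as written, allows harms of the randomised intervention to go unrecorded, unattributed and unreported as study AEs, against section 7.1.1 and the unqualified monitoring in sections 8.1 and 5.4 and Table 1. Capture is not assured; the documents do not show that it is impossible.

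The size is one of scope and cannot be expressed as a rate. It concerns bed-related events in both arms, since all children in the planned 50 dyads are due to receive a bed. It does not touch the sleep endpoints or their analysis. The conclusion rests on reading the specific sentence in 8.2 as overriding the general ones. If the sponsor meant only to assign responsibility for the product, the text still has to say so.

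**What to change.** Delete the last sentence of section 8.2. State once, in section 8, that AEs related to the bed or bedding are study AEs, recorded at the AE assessments already in Table 1 and reported to the IRB under the same SOP as other events. Then bring the other provisions into line:

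- **Section 4.4:** families may still go to the charity about replacement materials, but the study team records any associated AE.
- **Section 9.4.1:** a bed-related event learned of at the monthly check-in is recorded as an AE where it can be linked to a participant.
- **Sections 7.1.1 and 8.1 and Table 1:** the same definition of the intervention and of a study AE applies in each.
- **Section 6:** add a descriptive listing of AEs by arm and by time relative to bed delivery, without testing.
- **Section 9.4.2:** address bed-related risk, so that section 9.4.4 weighs both sides.

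The cost is one sentence removed, a few aligned, and one added question on calls that already take place, with slightly more AE recording. Allocation, visits and efficacy analyses do not change.
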